### 8.1 Definitions

#### Unanticipated Problems Involving Risk to Subjects or Others (UPIRTSO)

Any unanticipated problem or adverse event that meets the following three criteria:

- Serious: Serious problems or events that results in significant harm (which may be physical, psychological, financial, social, economic, or legal) or increased risk for the subject or others (including individuals who are not research subjects). These include: (1) death; (2) life threatening adverse experience; (3) hospitalization - inpatient, new, or prolonged; (4) disability/incapacity - persistent or significant; (5) birth defect/anomaly; (6) breach of confidentiality; and (7) other problems, events, or new information (*i.e.* publications, DSMB reports, interim findings, product labeling change) that in the opinion of the local investigator may adversely affect the rights, safety, or welfare of the subjects or others, or substantially compromise the research data, **AND**
- Unanticipated: (*i.e.*, unexpected) problems or events are those that are not already described as potential risks in the protocol, consent document, not listed in the Investigator's Brochure, or not part of an underlying disease. A problem or event is "unanticipated" when it was unforeseeable at the time of its occurrence. A problem or event is "unanticipated" when it occurs at an increased frequency or at an increased severity than expected, **AND**
- Related: A problem or event is "related" if it is possibly related to the research procedures.

#### Adverse Event

An untoward or undesirable experience associated with the use of a medical product (*i.e.*, drug, device, biologic) in a patient or research subject.

## **Serious Adverse Event**

Adverse events are classified as serious or non-serious. Serious problems/events can be well defined and include:

- An outcome of death
- An immediate life-threatening adverse experience
- Inpatient hospitalization or prolongation of existing hospitalization \*Emergency room visits that do not result in admission to the should be evaluated for one of the other serious outcomes (e.g., life-threatening; required intervention to prevent permanent impairment or damage; other serious medically important event).
- Persistent or significant disability or incapacity; an event that results in significant, persistent, or permanent change, impairment, damage, or disruption of the subject's body function/structure, physical activities, and/or quality of life.
- Substantial disruption of the ability to conduct normal life functions
- Exposure to a medical product prior to conception of during pregnancy resulting in a birth defect/congenital anomaly and/or according to the protocol may be problems/events that in the opinion of the sponsor-investigator may have adversely affected the rights, safety, or welfare of the subjects or others, or substantially compromised the research data.

All adverse events that do not meet any of the criteria for serious, should be regarded as **non-serious adverse events**. For this study, such non-serious events would include changes in clinical status that would cause a subject to meet our exclusion criteria at some point after enrollment.

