#### **4.2.2 Laboratory Exclusion Criteria:**

The following laboratory tests as indicated or as *per* clinical judgement:

- Bilirubin > 2.0; serum aspartate transaminase (AST) > 4 X upper limit of normal, or alanine aminotransferase (ALT) > 4 X upper limit of normal as a marker of liver disease
- Hemoglobin < 7g/dL; white blood cell count  $\leq$  2,000/mm^3 ( $\leq$  2.0 x 10^9/L) or  $\geq$  20,000/mm^3 ( $\geq$  20 x 10^9/L); platelet count  $\leq$  40,000/ $\mu$ L ( $\leq$  40 x 10^9/L); absolute neutrophil count  $\leq$  1 x 10^9/L; lymphocyte count  $<$  0.3 x 10^9/L at screening as a marker of poor nutrition
- Plasma and/or serum fasting glucose > 300 or HbA1c > 9 as a marker of poor diabetic control
- Creatinine > 2.5, cystatin c > 3 or eGFR < 25 ml/min/1.73 m^2 as a marker of advanced kidney disease,
- CRP > 10 or ESR > 25 as a marker of systemic inflammation
- Unstable (as per clinical judgement) major cardiovascular, renal, endocrine, immunological, or hepatic disorder

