#### **4.2.3 Clinical History Exclusion Criteria**

- History of diverticulitis or diverticulosis with GI bleeding, as *per* clinical judgement
- Any of the following clinical diagnosis or conditions: cervical radiculopathy, renal failure (see laboratory exclusion criteria), liver disease (see laboratory exclusion criteria), peripheral nerve disease, uncontrolled diabetes (see laboratory exclusion criteria), or other metabolic disorder; as *per* clinical judgement
- Human immunodeficiency virus infection
- Known active hepatitis B or C infection
- Invasive fungal infection
- Uncontrolled (as per clinical judgement) pleural/pericardial effusions or ascites
- New/active invasive cancer except non-melanoma skin cancers

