### **Hospitalization, Prolonged Hospitalization, or Surgery**

Any adverse event that results in hospitalization or prolonged hospitalization should be documented and reported as a serious adverse event unless specifically instructed otherwise in this protocol. Any condition responsible for surgery should be documented as an adverse event if the condition meets the criteria for an adverse event.

Neither the condition, hospitalization, prolonged hospitalization, nor surgery are reported as an adverse event in the following circumstances:

The following hospitalizations will not be considered SAE for this study:

- a visit to the emergency department or other hospital department <24 hours, that does not result in admission (unless considered an important medical or life-threatening event). However, the reason for the ER visit should be considered/recoded as an adverse event
- elective surgery planned prior to signing consent
- admissions according to the protocol for a planned medical/surgical procedure
- routine health assessment requiring admission for baseline/trending of health status (e.g., routine mammogram)
- medical or surgical admission other than to remedy ill health and planned prior to entry into the study. Appropriate documentation will be obtained in these cases

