### 8.3.1 Sponsor-Investigator Reporting: Notifying the Mayo IRB

The sponsor-investigator will report to the Mayo IRB any UPIRTSOs and Non-UPIRTSOs according to the Mayo IRB Policy and Procedures.

Information collected on the adverse event worksheet (*and entered in the research database*):

- Subject's name
- The date the adverse event occurred
- Description of the adverse event
- Relationship of the adverse event to the research drug: Not Related, Possibly Related, Probably Related, or Related
- If the adverse event was expected
- The severity of the adverse event: (Mild, symptoms such as GI upset, nausea, or headache; Moderate, symptoms such as vomiting, vertigo, chest pain; Severe, any problem requiring more than one day of OTC medication, or requiring a doctor visit, such as chest pain, vertigo, GI bleeding, *etc*)
- If any intervention was necessary/action taken
- Resolution: was the incident resolved spontaneously or after discontinuing treatment
- Date of Resolution

The Investigator will review all adverse event reports to determine if specific reports need to be made to the IRB and FDA. The sponsor-investigator will sign and date the adverse event report when it is reviewed. For this protocol, only directly related SAEs/UPIRTSOs will be reported to the IRB. Non-UPIRTSOs/non-serious AEs will be reported at the time of annual continuing review, according to the IRB policy.

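### Section 8.1 is ambiguous on seriousness: it offers exclusion-criterion changes as examples of non-serious events and gives medically important events no clear criterion, so major outpatient toxicity found after dosing could be left out of SAE reporting and the SAE count

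*Combined protocol and SAP*

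**What the plan says.** **The definition (8.1, Serious Adverse Event).** The bullets cover death; immediate threat to life; new or prolonged admission; persistent or significant disability, including significant impairment of body function; substantial disruption of normal life; and birth defect after exposure. The last bullet then runs on into a clause about problems that, in the sponsor-investigator's opinion, affected subjects' rights, safety or welfare.

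A note inside the admission bullet tells sites to evaluate emergency-room visits without admission for other serious outcomes, among them "required intervention to prevent permanent impairment or damage; other serious medically important event". A later part of 8.1, on hospitalization, leaves short hospital visits out of the SAE category "unless considered an important medical or life-threatening event".

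Two closing sentences follow the bullets. The first begins "All adverse events that do not meet any of the criteria for serious, should be regarded as" and ends with the non-serious label. The second says "For this study, such non-serious events would include changes in clinical status that would cause a subject to meet our exclusion criteria".

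**The exclusion criteria referred to.** Section 4.2.2 lists hemoglobin below 7 g/dL, platelets at or below 40 x 10^9/L, neutrophils at or below 1 x 10^9/L, AST or ALT above 4 times the upper limit of normal, eGFR below 25, and "Unstable (as per clinical judgement) major cardiovascular, renal, endocrine, immunological, or hepatic disorder". Section 4.2.3 lists invasive fungal infection and "New/active invasive cancer except non-melanoma skin cancers".

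**What depends on the label.** Section 8.2 requires immediate reporting of SAEs that are at least possibly related. Section 8.3.2 sets FDA deadlines of 7 or 15 calendar days for unexpected serious suspected reactions. The toxicity stopping rule in 8.5 ends the study when SAEs exceed 3. For the IRB, 8.3.1 says "Non-UPIRTSOs/non-serious AEs will be reported at the time of annual continuing review".

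**The concern.** The closing remark is the only place where 8.1 gives study-specific examples, and its examples of non-serious events include findings that many readers would want assessed as possibly serious. An outpatient with severe cytopenia or a newly diagnosed cancer may not have died, been admitted, been in immediate danger or been disabled. Such an event would qualify as serious mainly as a medically important event, and that is the criterion without a clear entry in the list. The two drafting faults therefore act together: the most relevant route to serious is hard to find, and the next sentence points towards non-serious.

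At stake are the timeliness of safety reports and the SAE count in the toxicity stopping rule. Section 8.6.1 provides for no formal DSMB, so classification rests with the investigator reading this definition.

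**Working it through.** The documents state no operating characteristic for the SAE rule, so there is no planned figure to reproduce. The check is mainly textual.

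**1. Take one case through the definition.** Suppose an eligible subject, well and at home, has platelets of 35 x 10^9/L at the Day 45 safety labs.

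| Part of the definition | Result |
|---|---|
| Death, immediate threat to life, admission | Not met |
| Emergency-room note (required intervention, medically important) | Not reached: there was no emergency visit |
| Disability or significant impairment of body function | Arguable |
| Substantial disruption of normal life | Not met |
| Birth-defect bullet with fused catch-all | Unclear whether the catch-all stands alone |
| Closing remark | 35 is below the limit of 40 in 4.2.2, so the case fits the non-serious example |

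Two careful readers could classify this case differently.

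**2. See which safeguards reach it.**
- *Pause for a severe event (8.5).* It is tied to administration of the 2-day regimen, on Days 0, 1, 29 and 30. The last dose may be as late as Day 30 + 2 = 32, and the Day 45 visit as early as 45 - 5 = 40. The gap is at least 40 - 32 = 8 days, so the finding lies outside the pause.
- *Individual stopping rule (8.5).* Meeting an exclusion criterion stops study drug. After the last dose nothing is left to stop, and the rule triggers no report.
- *Abnormal laboratory values (8.1).* The value becomes an adverse event with clinical follow-up. That follow-up does not settle seriousness.
- *Investigator review (8.3.1) and the unanticipated-problem definition (8.1).* Both can still bring the event to the IRB, at the investigator's discretion.

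For the labs drawn up to 5 days before Visit 3A, the individual stopping rule does have effect, so the gap is smaller there.

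**3. Illustrate the effect on the count.** Inputs from the documents: 40 subjects enrolled (Study Summary) and termination when SAEs exceed 3, that is at 4 or more (8.5). Assumed: a per-subject risk *p* of a serious event, a share *f* of those events labelled non-serious, at most one event per subject, and all 40 followed. Then

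P(rule met) = P(X >= 4), with X ~ Binomial(40, p(1 - f)).

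| p (assumed) | f = 0 | f = 0.25 | f = 0.50 |
|---|---|---|---|
| 5% | 0.138 | 0.062 | 0.017 |
| 10% | 0.577 | 0.353 | 0.138 |
| 15% | 0.870 | 0.673 | 0.353 |
| 20% | 0.972 | 0.870 | 0.577 |

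At p = 10% and f = 0.50 the counted rate is 0.10 x 0.50 = 5%, which is why that entry equals the 5% row at f = 0. The table shows how sensitive the rule is to labelling. It does not predict how often mislabelling would occur.

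**The case against.** The case against is substantial, and most of it stands.

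- **The remark does not override the criteria.** A reader might infer that every exclusion-type change is declared non-serious in advance. The text does not support that: "such" events are those that have already failed every serious criterion. An exclusion-type event that leads to death or admission remains serious. Several exclusion lines, such as CRP above 10 or ESR above 25, are not obviously serious anyway.
- **The two outcomes are not absent.** They are named as serious in the emergency-room note, so an allergic reaction treated in the emergency department and sent home is exactly what the note asks sites to evaluate. What is missing is a criterion that applies without an emergency visit.
- **Other routes exist.** The list is introduced as inclusive, the disability bullet extends to significant impairment of body function, and the catch-all is present though garbled. PDF extraction may have merged bullets.
- **Seriousness does not control every safety action.** The pause depends on severity, which 8.3.1 sets at a low threshold. The individual stopping rule covers exclusion criteria directly. All adverse event reports are reviewed by the investigator, and 8.6 and 8.6.1 do not confine monitoring to serious events.
- **Annual review is not the only path to the IRB.** The unanticipated-problem definition has its own seriousness test, including an investigator-opinion item. Nor can one say that a report slips from 15 days to a year: the first is an FDA deadline and the second an IRB cycle.

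These points narrow the gap but leave it open for toxicity found in an outpatient after the last dose, where classification rests on an unclear list and an example pointing the other way.

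**Conclusion.** The definition is ambiguous and should be reworded. The exposure is limited to major laboratory or organ toxicity that causes no death, immediate threat to life, admission or disability, chiefly when found at the Day 45 or Day 60 labs. Such an event could be labelled non-serious and so be left out of immediate SAE reporting (8.2), FDA expedited reporting (8.3.2, if also unexpected and suspected to be related) and the SAE count (8.5).

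The documents do not allow the frequency to be estimated. The loss in the chance of meeting the stopping rule, for example from 0.577 to 0.138, rests wholly on the assumed *p* and *f*. It is zero if sites classify correctly, and section 1.6 anticipates no serious events. The broader inference that major toxicity would escape review altogether is not supported, because adverse event capture, laboratory follow-up and investigator review remain. That places the point at should-fix.

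**What to change.** Three wording changes in 8.1, carried into the adverse event worksheet:

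1. Replace the closing remark with: *A change that makes a subject meet an exclusion criterion is an adverse event; its seriousness is judged by the criteria above.*
2. Give the two outcomes that the protocol already uses, required intervention to prevent permanent impairment and medically important event, their own bullets, so that they apply with or without an emergency-room visit.
3. Separate the investigator-opinion catch-all from the birth-defect bullet.

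The cost is a protocol wording amendment and a few more events classified as serious and reported promptly. No dose, schedule or stopping threshold changes.

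In the same amendment, the sponsor should reconcile the use of severe and serious. Section 4.4.1 expands SAE as a severe event and attaches a hold to three or more events. Section 8.5 pauses on a severe event and terminates when SAEs exceed 3.

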## **Adverse Event Reporting Period**

For this study, the treatment period is defined as 30 ( $\pm 2$ ) days. The adverse event reporting period ends when the subject completes the study.

## **Preexisting Condition**

A preexisting condition is one that is present at the start of the study. A preexisting condition should be recorded as an adverse event if the frequency, intensity, or the character of the condition worsens during the study period.

## **General Physical Examination Findings**

At screening, any clinically significant abnormality should be recorded as a preexisting condition. At the end of the study, any new clinically significant findings/abnormalities that meet the definition of an adverse event must also be recorded and documented as an adverse event.

## **Post-study Adverse Event**

All unresolved adverse events should be followed by the sponsor-investigator until the events are resolved, the subject is lost to follow-up, or the adverse event is otherwise explained. At the last scheduled visit, the sponsor-investigator should instruct each subject to report, to the sponsor-investigator, any subsequent event(s) that the subject, or the subject's personal physician, believes might reasonably be related to participation in this study.

## **Abnormal Laboratory Values**

A clinical laboratory abnormality will be documented as an adverse event if it changes from a value within the normal range (or as *per* clinical judgement) before treatment to one outside and worse than the normal range after treatments. Such changes will prompt a repeat test, telephone call to check the subject's status, a repeat visit, and/or referral to the subjects' primary care physician.

### **Hospitalization, Prolonged Hospitalization, or Surgery**

Any adverse event that results in hospitalization or prolonged hospitalization should be documented and reported as a serious adverse event unless specifically instructed otherwise in this protocol. Any condition responsible for surgery should be documented as an adverse event if the condition meets the criteria for an adverse event.

Neither the condition, hospitalization, prolonged hospitalization, nor surgery are reported as an adverse event in the following circumstances:

The following hospitalizations will not be considered SAE for this study:

- a visit to the emergency department or other hospital department <24 hours, that does not result in admission (unless considered an important medical or life-threatening event). However, the reason for the ER visit should be considered/recoded as an adverse event
- elective surgery planned prior to signing consent
- admissions according to the protocol for a planned medical/surgical procedure
- routine health assessment requiring admission for baseline/trending of health status (e.g., routine mammogram)
- medical or surgical admission other than to remedy ill health and planned prior to entry into the study. Appropriate documentation will be obtained in these cases

## **8.2 Recording of Adverse Events**

At each contact with the subject, the study team must seek information on adverse events by specific questioning and, as appropriate, by examination. Information on all adverse events should be recorded immediately in the source document, and also in the appropriate adverse event section of the case report form (CRF) or in a separate adverse event worksheet. All clearly related signs, symptoms, and abnormal diagnostic, laboratory, or procedure results should be recorded in the source document.

All adverse events occurring during the study period must be recorded. The clinical course of each event should be followed until resolution, stabilization, or until it has been ultimately determined that the study treatment or participation is not the probable cause. Serious adverse events that are still ongoing at the end of the study period must be followed up, to determine the final outcome. Any serious adverse event that occurs during the Adverse Event Reporting Period and is considered to be at least possibly related to the study treatment or study participation should be recorded and reported immediately.

## **8.3 Reporting of Serious Adverse Events and Unanticipated Problems**

When an adverse event has been identified, the study team will take appropriate action necessary to protect the study participant and then complete the Study Adverse Event Worksheet and log. The sponsor-investigator will evaluate the event and determine the necessary follow-up and reporting required.

### 8.3.1 Sponsor-Investigator Reporting: Notifying the Mayo IRB

The sponsor-investigator will report to the Mayo IRB any UPIRTSOs and Non-UPIRTSOs according to the Mayo IRB Policy and Procedures.

Information collected on the adverse event worksheet (*and entered in the research database*):

- Subject's name
- The date the adverse event occurred
- Description of the adverse event
- Relationship of the adverse event to the research drug: Not Related, Possibly Related, Probably Related, or Related
- If the adverse event was expected
- The severity of the adverse event: (Mild, symptoms such as GI upset, nausea, or headache; Moderate, symptoms such as vomiting, vertigo, chest pain; Severe, any problem requiring more than one day of OTC medication, or requiring a doctor visit, such as chest pain, vertigo, GI bleeding, *etc*)
- If any intervention was necessary/action taken
- Resolution: was the incident resolved spontaneously or after discontinuing treatment
- Date of Resolution

The Investigator will review all adverse event reports to determine if specific reports need to be made to the IRB and FDA. The sponsor-investigator will sign and date the adverse event report when it is reviewed. For this protocol, only directly related SAEs/UPIRTSOs will be reported to the IRB. Non-UPIRTSOs/non-serious AEs will be reported at the time of annual continuing review, according to the IRB policy.

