### **3.6 Primary Safety Endpoints**

Safety endpoints are undertaken with the measurement of safety laboratory testing, adverse event monitoring, and subject questionnaires.

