## 8.5 Stopping Rules

All subjects will be assessed during the 2 cycles each lasting for 2 days of Fisetin administration (after Visits 1 and 2; total 4 days) and during each visit following administration of the first cycle of drugs. If a severe adverse event occurs at any time during administration of the 2-day drug regimen, the study will pause, and a formal review will occur. Subsequent subjects will only be enrolled if the SAE is determined to be unrelated to the study drug. Other interventions will be as according to the direction of the FDA and Mayo IRB.

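### The severity scale in 8.3.1 lets one adverse event meet two grades with no rule on which prevails, and 4.4.1 and 8.5 leave unclear whether that grade triggers the study review or pause

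*Combined protocol and SAP*

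**What the plan says.** The adverse event worksheet described in section 8.3.1, whose contents are entered in the research database, asks for one of three severity grades:

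- Mild: "Mild, symptoms such as GI upset, nausea, or headache".
- Moderate and Severe, which follow one another: "Moderate, symptoms such as vomiting, vertigo, chest pain; Severe, any problem requiring more than one day of OTC medication, or requiring a doctor visit". The examples then given for Severe are "such as chest pain, vertigo, GI bleeding".

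No other severity scale appears in the documents, and no sentence says how to grade an event that fits two descriptions.

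The word severe returns in two trial-level rules. Section 8.5 says "If a severe adverse event occurs at any time during administration of the 2-day drug regimen, the study will pause", and its next sentences call for a formal review and allow further enrolment only if the SAE is judged unrelated to the drug. Section 4.4.1 starts from the same kind of event but prescribes a formal review with one-at-a-time enrolment, and a hold once three or more events have accrued. It abbreviates severe adverse event as SAE. The List of Abbreviations expands SAE as serious, and section 8.1 defines serious by outcomes such as death, life-threatening events, hospitalization or disability, not by the 8.3.1 grade.

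**The concern.** The scale uses two different yardsticks. The lower two grades depend on what the symptom is; the top grade depends on what care it needs. Mild and Moderate have no upper limit, and Severe takes in any problem that meets its care criterion, so the categories are not exclusive.

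Two things are at stake. First, the recorded grade may not be reproducible: two coordinators, or one grader at different times, can apply the text faithfully and record different grades for the same event. Second, if the trigger in 4.4.1 and 8.5 means the top severity grade, the ambiguity carries over into a decision about the whole trial. A minor complaint that needs more than a day of OTC treatment could start the review or pause, and a symptom recorded as Moderate because it is listed there would not.

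**Working it through.** The plan gives no figure for this point, so there is none to reproduce. The check sets the definitions against each other and then against the trigger.

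**Step 1: grade some cases by the text of 8.3.1.**

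| Event | Grade by listed symptom | Grade by care criterion |
|---|---|---|
| Headache requiring OTC medication into a second day | Mild | Severe |
| Vomiting requiring OTC medication into a second day | Moderate | Severe |
| Chest pain requiring a doctor visit | Moderate, and also named under Severe | Severe |
| Vertigo requiring neither | Moderate, and also named under Severe | Not met |

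The first three events satisfy two grades at once. In the fourth, the Severe wording, "requiring a doctor visit, such as chest pain, vertigo, GI bleeding", most naturally treats vertigo as an example of a problem that needs a visit, which leaves Moderate. A grader working from the two symptom lists alone could still choose either.

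**Step 2: follow the grade into the trigger, for events during a 2-day course.**

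- Trigger read as the severity grade: the headache in row 1 starts the 8.5 pause and the 4.4.1 review if graded Severe, and starts neither if graded Mild. Chest pain recorded as Moderate starts neither.
- Trigger read as the serious classification: the 8.3.1 grade has no role. Only an event meeting the outcome criteria in 8.1 counts.

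The documents support both readings. 8.5 and 4.4.1 both write severe; both also write SAE, which the abbreviation list expands as serious.

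**Step 3: illustration of what the literal reading could mean.** Inputs: n = 40 (Study Summary), and p, the probability that a subject has at least one event during either course that meets the Severe description. The documents give no value for p, so it is assumed over a range, with subjects independent and one event counted per subject.

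P(at least 1) = 1 − (1 − p)^40

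P(at least 3) = 1 − (1 − p)^40 − 40p(1 − p)^39 − 780p²(1 − p)^38

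| Assumed p | At least 1 (pause in 8.5) | At least 3 (hold in 4.4.1) |
|---|---|---|
| 1% | 33% | 0.7% |
| 2% | 55% | 4.6% |
| 5% | 87% | 32% |
| 10% | 98.5% | 78% |

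For example, at p = 5%: 1 − 0.95^40 = 1 − 0.129 = 0.871. If the same events are graded Mild or Moderate, they contribute nothing to either count.

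**The case against.** The strongest defence is that the Severe wording works as an override: any problem that requires the stated care is Severe, and otherwise the symptom lists apply. On that reading vertigo is Moderate unless it needs a doctor visit, and most of the overlap disappears. The text also says requiring, which is a higher bar than simply taking a product for two days. This is a fair reading, and it means that the scale is not useless. But it is not written down, and under it nausea needing two days of OTC medication ranks above chest pain or vomiting that needed no care, so the mixture of axes remains.

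Several stronger readings are tempting and should not be adopted:

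- A reader might infer that different sites would grade differently. The Study Summary describes a single-site study, and under 8.3.1 the investigator reviews every adverse event report and the sponsor-investigator signs it. That review limits inconsistency, although it applies the same unclear text.
- A reader might infer that a primary safety endpoint is compromised. Section 3.6 says only "Safety endpoints are undertaken with the measurement of safety laboratory testing, adverse event monitoring, and subject questionnaires"; it does not name severity, and section 7 plans no analysis by grade.
- A reader might infer that the top grade definitely pauses the trial. That holds only if severe is meant literally. The pause also concerns only events during the 2-day courses.
- A reader might infer that chest pain could escape all safety rules. Chest pain requiring a doctor visit meets the Severe criterion, and if it is life-threatening or leads to hospitalization it is serious under 8.1 whatever its grade, which ends study drug for that subject under the individual stopping rules in 8.5.

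**Conclusion.** The concern holds in a limited form. The 8.3.1 scale mixes symptom type with care required, names two symptoms under two grades, lets the Mild examples also meet Severe, and gives no precedence rule. The recorded grade can therefore vary between graders or over time. This conclusion needs no numerical assumption.

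The effect on the conduct of the trial is conditional. It exists if severe in 4.4.1 and 8.5 refers to the severity grade, and vanishes if serious was meant; the documents do not settle which. Under the literal reading, the chance of at least one triggering event runs from 33% to 98.5% as the assumed per-subject rate goes from 1% to 10%. Those percentages show only how sensitive the trigger would be to the grading choice; they are not estimates for this trial. The efficacy analysis and sample size are untouched. The point should be corrected because the definition is a safety rule, the correction is cheap, and 8.6.1 provides no formal DSMB, leaving adverse event monitoring to the principal investigator.

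**What to change.** Reconcile sections 4.4.1, 8.1, 8.3.1 and 8.5 together:

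1. In 8.3.1, either define the three grades on one stated axis so that they are mutually exclusive, or keep the present descriptions and add an explicit rule for an event that meets two of them. A symptom may appear at more than one grade if the axis separates the cases; restricting each symptom to a single grade is not needed and would tie severity to symptom type.
2. In 4.4.1 and 8.5, state whether the trigger is the severity grade or the serious classification, and use one term and one expansion of SAE throughout.

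The clinical content of the grades and of the trigger is for the investigator to settle. The cost is a paragraph in 8.3.1, matching wording in 4.4.1 and 8.5, and one worksheet field. The small downside is that events already recorded would need to be re-graded.
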